### 3.4.5 Laboratory Evaluations

#### Hematology

Hematology must include hemoglobin, hematocrit, platelets, total white blood cell count (WBC) and differential. PT (INR) evaluation will be included for baseline evaluations.

#### Blood chemistry

Blood chemistry must include sodium, potassium, chloride, bicarbonate, calcium, glucose, creatinine, blood urea nitrogen, albumin, total protein, SGOT (AST), SGPT (ALT), total bilirubin, alkaline phosphatase, uric acid, phosphorus, serum lipid profile (triglycerides, total cholesterol, HDL and LDL).

Because accurate serum glucose and lipid measurements are required, patients should be fasting at the time of the blood sampling.

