The use of live vaccines and close contact with those who have received live vaccines should be avoided during treatment with everolimus. **Close contact with those who have received attenuated live vaccines should be avoided during treatment with everolimus. Examples of live vaccines include intranasal influenza, measles, mumps, rubella, oral polio, BCG, yellow fever, varicella and TY21a typhoid vaccines.**

Hypophosphatemia, hypomagnesemia, hyponatremia and hypocalcemia have been reported as serious adverse reactions. Electrolytes should be monitored in patients treated with Everolimus.

**Table 3-1** provides general recommendations for the management of patients, with suspected drug toxicities while on treatment with Everolimus as single-agent therapy.

More detailed information regarding Everolimus reported suspected toxicities and individual cases is provided in the [Investigator's Brochure](#).

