### **3.2.5.2 Management of hyperlipidemia and hyperglycemia**

Treatment of hyperlipidemia should take into account the pre-treatment status and dietary habits. Blood tests to monitor hyperlipidemia must be taken in the fasting state. Treatment of hyperlipidemia should take into account the pre-treatment status and dietary habits. Blood tests to monitor hyperlipidemia must be taken in the fasting state.. Hyperlipidemia and hypertriglyceridemia should be treated according to local best clinical practice. Patients should be monitored clinically and through serum chemistry for the development of rhabdomyolysis and other adverse events as required in the product label/data sheets for HMG-CoA reductase inhibitors.

Hyperglycemia has been reported in clinical trials. Monitoring of fasting serum glucose is recommended prior to the start of everolimus therapy and periodically thereafter. Optimal glycemic control should be achieved before starting trial therapy.

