### 3.4.2 Visit schedule

**Table 3-4 Evaluation and visit schedule**

Examination	Screening/ Baseline	Week									
		4	16	32	52	64	80	96	112	128	144
Informed consent	X										
No Evidence of Disease	X										
Inclusion/exclusion criteria	X										
Tissue Biopsy	X										
Radiographic assessment	X										
Physical examination	X										
ECG	X										
Laboratory test	X	X	X	X	X	X	X	X	X	X	X
Research Blood Draw	X	X	X		X						
HBV-DNA, HbsAg, HBs Ab, HBs Ab, HCV-RNA-PCR^6	X										
Patient Questionnaire	X										
Follow Up Form^8		X	X	X	X	X	X	X	X	X	X

See Section 3.2.2

See Section 3.4.7; Tissue biopsy must have been obtained PRIOR to curative intent therapy

Baseline radiographic assessment (CT, PET-CT, PET and/or MRI as appropriate) must be preformed within 12 weeks of starting everolimus. CT, PET-CT, PET and/or MRI as appropriate should be performed at least every 4-6 months in years 1 and 2 then every 6 months in year 3.

Baseline assessments must be performed within 7 days of starting everolimus. Hemoglobin, platelets, total white blood cell count (WBC), and differential; sodium, potassium, chloride, bicarbonate, calcium, glucose, creatinine, blood urea nitrogen, albumin, total protein, SGOT (AST), SGPT (ALT), total bilirubin, alkaline phosphatase, uric acid, phosphorus, serum lipid profile (triglycerides, total cholesterol, HDL and LDL); PT (INR) evaluation only at baseline unless otherwise indicated. Patients should be fasting at the time of the blood sampling.

Blood draw for serum, whole blood and optional PBMC isolation (see Section 3.4.7). Serum will be drawn at screening, weeks 4, 16 and 52. Whole blood will be drawn at weeks 4, 16 and 52. Optional PBMC will be drawn at screening and week 4.

All patients should be **screened** for hepatitis risk factors and any past illnesses of hepatitis B and hepatitis C infection. If the patient has any of the risk factors outlined in section 3.4.1 then serologic testing must be done.

All patients should fill out the Patient Questionnaire prior to first dose. See the Study Procedures manual.

See the Study Procedures Manual

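### Hypomagnesemia is named as a serious everolimus reaction, but magnesium is missing from both required chemistry lists, so no scheduled visit requires it

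*Combined protocol and SAP*

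**What the plan says.** Section 3.2.5 (Known Undesirable Side Effects of Everolimus) names four electrolyte disturbances: "Hypophosphatemia, hypomagnesemia, hyponatremia and hypocalcemia have been reported as serious adverse reactions". It then says: "Electrolytes should be monitored in patients treated with Everolimus". It does not say which electrolytes or how often.

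Two places turn this into scheduled tests. Section 3.4.5, under Blood chemistry, says: "Blood chemistry must include sodium, potassium, chloride, bicarbonate, calcium, glucose, creatinine, blood urea nitrogen, albumin, total protein, SGOT (AST), SGPT (ALT), total bilirubin". The list goes on to alkaline phosphatase, uric acid, phosphorus and the lipid profile. Footnote 4 to Table 3-4 gives the same chemistry items in the same order and ends in the same way: "alkaline phosphatase, uric acid, phosphorus, serum lipid profile (triglycerides, total cholesterol, HDL and LDL". Table 3-4 marks this laboratory test at screening/baseline and at weeks 4, 16, 32, 52, 64, 80, 96, 112, 128 and 144.

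Toxicity of everolimus against placebo is the first secondary objective in section 2. Section 6.1 compares adverse event rates between arms by a chi-squared or Fisher's exact test.

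**The concern.** The risk section and the laboratory schedule should agree, because the schedule is what sites carry out. Here the risk section names four disturbances and the schedule tests for three. A site that follows the plan to the letter produces no magnesium result for any patient at any time.

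Two things are at stake. The first is patient safety. Table 3-1 ties action on study drug to toxicity grade, and a disturbance that nobody measures cannot be graded. The annual DSMB toxicity review in section 4.7 would likewise have no systematic magnesium data. The second is the toxicity comparison. For hypomagnesemia it would rest on whichever sites chose to test and whichever patients had symptoms, not on uniform ascertainment.

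**Working it through.** No power, alpha or sample-size calculation is involved. The check is a cross-read of the risk text against the two laboratory lists, followed by a count.

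**Step 1. Named risks against required analytes**

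| Disturbance named in 3.2.5 | Analyte | In 3.4.5 list | In Table 3-4 footnote 4 |
|---|---|---|---|
| Hypophosphatemia | Phosphorus | Yes | Yes |
| Hyponatremia | Sodium | Yes | Yes |
| Hypocalcemia | Calcium | Yes | Yes |
| Hypomagnesemia | Magnesium | No | No |

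Coverage is 3 of 4 in each list. The two lists agree with each other, so the gap is not a slip in one place that the other corrects.

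**Step 2. Is magnesium added anywhere else?** Section 3.4.4 refers in general terms to regular blood chemistry monitoring and names no analyte. The research blood draws in section 3.4.7 are for correlative work. Table 3-1 sets actions once a toxicity is known and schedules no test. Nothing in the supplied text adds magnesium.

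**Step 3. Scheduled time points**

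- Screening/baseline: 1
- Treatment year (weeks 4, 16, 32, 52): 4
- After treatment (weeks 64, 80, 96, 112, 128, 144): 6
- Total: 1 + 4 + 6 = 11

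Magnesium is required at 0 of 11. Treatment lasts at most one year (sections 3.1 and 3.3.1), so the count that bears on drug exposure is 0 of 4. The other seven time points (1 + 6) fall before or after treatment. Patients who stop early will have fewer than four on-drug draws.

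**Step 4. Consequence for adverse event capture.** Section 3.4.4.1 counts an abnormal laboratory value as an adverse event only if it causes signs or symptoms, is judged clinically significant, or needs therapy. A symptomatic case can still be found without a scheduled test. A case that is clinically significant but silent has no routine way of being found. The same section counts a pre-existing condition only if it worsens on study drug. Without a baseline value, a low magnesium found later cannot be classified on that rule.

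**The case against.** The strongest reply has four parts.

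1. *The list is a minimum.* The wording of 3.4.5 sets what has to be included and does not bar more, and 3.4.4.1 records events detected by any means. This is correct, and it rules out a stronger reading that a reader might infer: that hypomagnesemia will go unmeasured throughout the trial. The documents support only that it is not required at any scheduled visit. The point survives in that form, because recording an event is not the same as looking for it, and optional testing leaves ascertainment uneven across sites.

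2. *The electrolyte instruction is largely met.* Three of the four named electrolytes are in the panel, together with potassium, chloride and bicarbonate. This is also correct, and it limits the point to one analyte. The protocol gives no reason for leaving out the fourth.

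3. *The effect on the toxicity comparison may be small.* The documents give no rate for hypomagnesemia. Section 3.2.5 does not list it among the reactions at 10% or more, or among the grade 3-4 reactions at 2% or more, in the renal cell carcinoma trial. Under 3.4.4.1, many silent low-grade values would not count as adverse events even if measured. This stands. A reader might infer that the trial will report hypomagnesemia as close to zero in both arms and so give false reassurance, but nothing in the documents yields that figure. Under-ascertainment of unknown size is what can be said.

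4. *Rhabdomyolysis is a separate matter.* Section 3.2.5.2 says: "Patients should be monitored clinically and through serum chemistry for the development of rhabdomyolysis and other adverse events", and adds "as required in the product label/data sheets for HMG-CoA reductase inhibitors". A reader might infer that the absence of creatine kinase from the panel is a second contradiction. The documents do not support this. They name no analyte for this purpose, the instruction combines clinical with chemistry monitoring, and its content is referred to statin labelling that is not part of the documents. That creatine kinase is the necessary marker would have to come from outside them. At most, the sponsor should reconcile 3.2.5.2 with the laboratory lists by saying how its serum-chemistry part is to be done.

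**Conclusion.** The mismatch on magnesium is real and can be checked from the protocol alone. One of four electrolyte disturbances reported as serious adverse reactions is absent from both required chemistry lists. It is required at none of the 11 scheduled laboratory time points, including the four in the treatment year. Hypomagnesemia would be under-ascertained, to a degree that depends on site practice and symptoms. That weakens safety monitoring and the between-arm toxicity comparison for this event alone.

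The conclusion rests on two assumptions: that sites run the required panel and do not uniformly add magnesium, and that no test is specified in material outside the supplied text. The number of missed cases cannot be estimated, since the documents give no incidence. The primary endpoint, the power and the sample size are unaffected. This is a modest point, worth correcting because the correction is cheap.

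**What to change.** Reconcile section 3.2.5 with section 3.4.5 and footnote 4 to Table 3-4. Add magnesium to both chemistry lists in identical words, at baseline and at the on-treatment draws (weeks 4, 16, 32 and 52). The baseline value is needed to tell a pre-existing low level from one that appears or worsens on study drug.

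The cost is one more analyte on blood already drawn: at most 1 + 4 = 5 assays per patient, or 160 × 5 = 800 over the trial, and fewer once early stopping is allowed for. No visit or venepuncture is added. The downside is the assay cost and some incidental low-grade findings that investigators must judge under 3.4.4.1.

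In the same amendment, the sponsor could state how the serum-chemistry part of the rhabdomyolysis instruction in 3.2.5.2 is to be met, or say that it is left to statin labelling.

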### 3.4.6 Vital signs

Vital sign assessment consists of height (first visit), pulse, blood pressure, respiration rate, temperature and weight.

### **3.4.6.1 Physical examination**

Physical examination will be performed which must comprise a total body examination (general appearance, skin, neck, including thyroid, eyes, ears, nose, throat, lungs, heart, abdomen, back, lymph nodes, extremities and basic nervous system).

Significant findings made after the start of study drug which meet the definition of an Adverse Event must be recorded.

### **3.4.6.2 ECG**

A standard 12 lead ECG is to be performed (during screening only to confirm I/E criteria) and significant findings must be recorded.

### **3.4.6.3 Performance status**

Performance status will be assessed using the Karnofsky scale

### **3.4.7 Research tests**

Tissue obtained (PRIOR to curative intent therapy) from the diagnostic biopsy/panendoscopy and/or during surgical resection, PBMC, serum and whole blood samples will be used for the correlative studies. The studies will be performed in [name] research laboratory (LSUHSC, Shreveport, LA) and at the University of Chicago.

The tumor suppressor gene PTEN is an important regulator of the Akt/mTOR pathway and often found to be mutated in HNSCC patients. Hence we will evaluate PTEN status by FISH and mutation analysis in all patients. Correlation between PTEN status and the sensitivity to Everolimus will be determined.

We will determine the correlation of the Akt/mTOR pathway activation [pAkt(S473), pmTOR(S2448), pS6(S235/236), p4EBP1(T37/46) and eIF4E] by IHC and/or western blot (when available) analysis in tumors and adjacent normal mucosa. The Kaplan-Meier method with logrank test and/or Cox Regression model will be used to compare PFS between HNSCC patients with different degree of biomarker upregulation in tumors but more importantly in the normal surrounding mucosa as previous studies have shown that patients with mTOR activation in the margins are at a higher risk for recurrence.

Upregulation of the Akt/mTOR pathway is associated with an increased survival of cancer cells and their decreased sensitivity to chemo- and radiotherapy. Also it was shown for some types of cancer that tumors with heightened Akt activation are more sensitive to mTOR inhibition. Based on these evidences we hypothesize that the risk of disease recurrence correlates with the degree of activation of the Akt/mTOR pathway biomarkers and that the patients with heightened Akt activation will benefit the most from adjuvant therapy with everolimus. Thus we will test the hypothesis that either the adjacent normal mucosa or tumor tissue or both from SCCHN patients who recurred after treatment will have higher pAkt/pmTOR expression as compared to the tissue samples from the SCCHN patients who did not recur after treatment.

#### **Tissue Sample:**

Diagnostic tumor biopsy should be preferably obtained from advancing edge of the tumor. Normal mucosa should be biopsied at least 1 cm away from the tumor.

At the minimum, **10 slides** of the tumor/biopsy and **10 slides** of all the histologically tumor free surgical resection margins/adjacent normal mucosa from the paraffin embedded blocks should be mounted on positively charged slides. Slides should be labeled with institution, protocol number, patient initials, patient registration number, and the date of biopsy. If tissue blocks are available these are preferable to the slides.

If frozen tissue obtained (PRIOR to curative intent therapy) from the diagnostic biopsy/panendoscopy and/or during surgical resection is available, resected tumor tissue and adjacent normal mucosa measuring minimum 1 cm x 5 mm should be placed in cryovials and clearly labeled with appropriate study identifiers. These samples should be stored at -80°C until shipment and they will be used for western blot biomarker analysis.

All tumor tissue should be accompanied by a de-identified pathology report and be shipped to LSUHSC in Shreveport for correlative studies at the address indicated below with accompanying Notification of Correlative Study Samples Shipment form (Appendix C).

**Peripheral Blood Mononuclear Cells (PBMC) (optional procedure based on the sites ability to process sample):**

Venous blood sample will be collected prior to therapy and at week 4 in 1 blue and black tiger top tube (~8 cc). See Appendix D for PBMC isolation protocol. Sample should be labeled with institution, protocol number, patient initials, patient registration number, and the date and time of draw. PBMC sample should be stored at -80°C till shipment. PBMC sample should be shipped with accompanying Sample Shipping Form and Notification of Correlative Study Samples Shipment form (Appendix C) to LSUHSC in Shreveport for correlative studies at the address indicated below. (As this is an adjuvant trial, patients will not have any post-treatment tumor tissue. Hence, biomarker changes in PBMC can be used as surrogate marker of tumor response.)

**Serum and whole blood:**

Serum samples will be collected prior to therapy on all patients and at weeks 4, 16 and 52 in three 7-10 cc gold top tubes. Blood in the serum collection tube should be allowed to clot for 60 minutes and then centrifuged to separate serum. Serum should be stored in 2 mL cryovial tubes (Nalgene Cat# 5000-0020) in 410uL aliquots. Samples should be labeled with institution, protocol number, patient initials, patient registration number, and the date and time of draw. Serum samples should be stored at -80°C till shipment. Serum samples collected from two gold top tubes should be shipped with a copy of accompanying Sample Shipping Form and Notification of Correlative Study Samples Shipment form (Appendix C) to LSUHSC in Shreveport for correlative studies at the address indicated below. Serum samples collected from one gold top tube should be shipped with accompanying Sample Shipping Form (Appendix C) to the University of Chicago at the address indicated below.

Whole blood samples will be collected on all patients at weeks 4, 16 and 52 in 1 lavender top tube (10 cc). The tube will be inverted several times to mix contents of the tube immediately after collection of the blood sample. Samples should be labeled with institution, protocol number, patient initials, patient registration number, and the date and time of draw. Freeze at

-80°C within 60 minutes of draw until shipment. Whole blood samples collected from one lavender top tube should be shipped with accompanying Sample Shipping Form (Appendix C) to the University of Chicago at the address indicated below.

We may store all samples until publication of the study results to potentially address reviewers concerns. It is not expected that any study samples will remain at the conclusion of the study as we have proposed an extensive number of biomarkers to analyze.

**Sample Shipping:**

All the tissue, PBMC, whole blood and serum samples will be packaged and transported by carrier service in batched samples following the government regulation 42 CFR Part 72 – “Interstate Shipment of Etiologic Agents,” which describes the requirements for the proper packaging and shipping of infectious substances and other biomedical material. All the samples will be packaged and delivered in such a way that the contents will not leak and will arrive in good condition. The tissue, PBMC, whole blood and serum samples will be transported in the packages with the biohazard label on the front to [name] laboratory or to [name] at the University of Chicago. Frozen tissue samples, PBMCs whole blood and serum samples should be shipped on dry ice. Paraffin-embedded tissue sections mounted on positively charged slides and paraffin-embedded tissue blocks should be shipped at ambient temperature. All institutional requirements for safety and confidentiality will be met during specimen transmittance. All samples must be accompanied by a Sample Shipping Form (Appendix C).

Correlative study investigator: (tissue, PBMC, 2 serum samples)	Research samples: (1 serum sample, whole blood)
[name], M.D., F.A.C.S.,	[name]
Department of Otolaryngology/HNS,	University of Chicago
Louisiana State University Health Sciences Center	[name]
[name]	[name]
[name]	[name]
[contact]; [contact]	[contact]
See Appendix C for further shipping instructions.	

## 4 Regulatory Procedures

### 4.1 New Protocol Distribution and IRB Submission

Once final Novartis and University of Chicago (U of C) IRB approval is received, the protocol and consent form will be distributed to the participating affiliate institutions electronically. Upon receipt of the email, the affiliate institution is expected to do the following:

- The affiliate must reply to the email indicating that the protocol was received by the institution.
- The affiliate institution is expected to submit the protocol to their IRB as soon as possible after receipt.
- **The U of C version date must appear on the affiliate consent form and on the affiliate IRB approval letter.** The version dates can be found on the footer of every page of the protocol and consent form.
- When the protocol and consent receive IRB approval at the affiliate institution **a copy of the IRB approval letter, the IRB approved protocol and the IRB approved consent form** must be faxed or emailed to the Regulatory Coordinator, [name] at [contact], [[contact]](mailto:[contact]).

#### **4.2 Amendment Distribution and IRB Submission**

Any change or addition (excluding administrative) to this protocol requires a written protocol amendment that must be reviewed by Novartis and the investigator before implementation. Amendments significantly affecting the safety of subjects, the scope of the investigation or the scientific quality of the study require additional approval by the IRB at each study center. A copy of the written approval of the IRB must be provided to Novartis. Examples of amendments requiring such approval are:

1. Increases in drug dose or duration of exposure of subjects,
2. Significant changes in the study design,
3. Increases in the number of invasive procedures,
4. Addition or deletions of a test procedure required for monitoring of safety.

These requirements for approval should in no way prevent any immediate action from being taken by the investigator or by Novartis in the interests of preserving the safety of all patients included in the trial. If an immediate change to the protocol is felt to be necessary by the investigator and is implemented for safety reasons Novartis must be notified and the IRB at the center must be informed immediately. Amendments affecting only administrative aspects of the study do not require formal protocol amendments or IRB approval but the IRB must be kept informed of such administrative changes. Examples of administrative changes not requiring formal protocol amendments and IRB approval include:

1. Changes in the staff used to monitor trials
2. Minor changes in the packaging or labeling of study drug.

All modifications to the protocol, or consent form will be submitted to the University of Chicago IRB for review and approval. A list of the proposed modifications or amendments to the protocol and an explanation of the need of these modifications will be submitted, along with a revised protocol incorporating the modifications. Only the P.I. at the central institution can authorize any modifications, amendments, or termination of the protocol. Once a protocol amendment has been approved by the U of C IRB, the Regulatory Coordinator will send the amended protocol and consent form to the affiliate institutions electronically. Upon receipt of the packet the affiliate institution is expected to do the following:

- The affiliate must reply to the email from the Regulatory Affairs Administrator indicating that the amendment was received by the institution and that it will be submitted to the local IRB.
- The amendment should be submitted to the affiliate institution's IRB as soon as possible after receipt. The amendment **must** be IRB approved by the institution **within 3 months** from the date that it was received.
- **The U of C version date and/or amendment number must appear on the affiliate consent form and on the affiliate IRB approval letter.** The version dates can be found on the footer of every page of the protocol and consent form. The amendment number can be found on the U of C IRB amendment approval letter that is sent with the protocol/amendment mailing.
- The IRB approval for the amendment and the amended consent form (if amended consent is necessary) for the affiliate institution must be faxed or emailed to the Regulatory Affairs Administrator.

